6.2 Study Drugs Administered

^{68}Ga -OPS202 is prepared, up to 3 hours prior to administration, by ^{68}Ga -radiolabelling of an OPS202 radiolabelling kit containing 50 μg of peptide.

6.3 Concomitant Medication/Therapy

Any relevant prior or concomitant therapy or medication given to a subject within 3 months before IIP administration, during IIP administration and up to the end of the follow-up period will be indicated in the eCRF. Dose and generic name or tradename will be recorded.

The following concomitant medications /therapies are not permitted during this study up to 48 hours post PET/CT scan:

- Administration of any radiopharmaceutical
- On Visit 2 parenteral amino acid solutions and any formulation of diuretics are not allowed. Stable adjusted diuretics such as for subjects with hypertension are permitted.

Long acting SSAs, ie, Somatuline® Autogel® /Depot® (60, 90 or 120 mg) and Sandostatin® LAR (20 or 30 mg) will not be allowed within 28 days prior to the ^{68}Ga -OPS202 PET/CT exam (at Visit 2). Short acting Sandostatin® is allowed during the study with a washout period of 24 hours before the ^{68}Ga -OPS202 PET/CT (Visit 2), to avoid possible interaction between the non-radioactive SSA and OPS202.

Other concomitant medications are permitted during this study at the discretion of the investigator; however, they must be monitored closely and every effort should be made to keep their dose and dose regimen constant throughout the course of the study.

6.4 Procedures for Monitoring Subject Compliance

The IIP is administered via the i.v. route by the investigator or his/her delegate. Therefore, no specific procedure is required for monitoring subject compliance. The injected peptide mass dose (calculated from the IIP volume) and radioactivity dose will be recorded in the medical file and in the eCRF for each subject.

The investigator will ensure that the subject did not take and is not taking any of the prohibited medication listed in Section 6.2 during the study period.

7 ASSESSMENT OF EFFICACY

For the primary, secondary and exploratory endpoints all the sets of images obtained at Visit 2 and one ^{18}F -FDG-PET and one ceCT scan will be sent to an ICL for quality control and management of the reads. The centralised reads will be undertaken by two independent experienced radiologists and/or nuclear medicine physicians, and a third for adjudication of discordances for most of the reads. The readers will be specifically trained for this protocol. Full details of the read design and conduct will be provided in the IRC.

For the primary endpoint analysis, the number of lesions and quality of the images will be taken into consideration by the readers. Scans will be blinded to subject identification, site and timing post injection. No adjudication will be conducted as inter-reader differences will be part of the evaluation.

The sequence of image display and recording of results will be as follows on a per subject basis:

- (1) Review of the three image sets of ^{68}Ga -OPS202 scans in randomised fashion, with CT image fusion. The ceCT images acquired will be used for co-registration. Two readers will read and a third will adjudicate any differences.
- (2) ^{18}F -FDG-PET images for standard-of-truth assessments will be reviewed by two radiologists not involved in ^{68}Ga -OPS202 PET/CT images read, and the lesions mapped to the ^{68}Ga -OPS202 read. Two readers will read and a third will adjudicate any differences.
- (3) SUV_{max} and SUV_{mean} calculations of the five most avid lesions per organ on ^{68}Ga -OPS202 PET scans (primary breast lesion, liver, lymph nodes, bone, lungs and brain) will be conducted by the ICL after identification of the lesions by one of the primary readers.
- (4) Review of the lesion-to-background ratios in each major anatomical site (primary breast lesion, liver, lymph nodes, bone, lungs and brain) based on the evaluation of up to five most avid lesions per organ will be managed by the ICL after the lesions have been identified by one of the primary readers.
- (5) For image quality, direct comparison of the three ^{68}Ga -OPS202 scans acquired at different times, will be conducted for the primary breast cancer and then for all other lesions as the final step of the blinded read. The readers will be allowed to select whether one, two or all three acquisitions are optimal. The readers will be blinded to time point sequence. No adjudication will be required.
- (6) The ^{68}Ga -OPS202 PET scans will be compared with the ^{18}F -FDG-PET scan (with ceCT).

(a) Primary Efficacy Endpoint and Evaluation

The co-primary endpoint is therefore calculated in the following way:

- (1) The number of subjects with newly diagnosed breast cancer with primary sstr2 positive lesions identified by ^{68}Ga -OPS202 at any timepoint, divided by the total number of subjects imaged to obtain the prevalence in this study population.
- (2) The identification of the optimum acquisition time(s) based on differences in the number of lesions identified at each scan, and the reader interpretation of the optimum image in the primary breast lesions. The optimum image acquisition time could be one, two or all three acquisitions timepoints i.e. no noticeable difference between 0.5, 1 and 2 hours post infusion.

(b) Secondary Efficacy Endpoints and Evaluations*Key Secondary Endpoint:*

- Differences in the number of lesions detected by ^{68}Ga -OPS202 between the three PET acquisition timepoints (0.5, 1 and 2 hours), and reader interpretation of optimal image(s) in nodular and metastatic lesions. Significant uptake of ^{68}Ga -OPS202 for the evaluation of a lesion is an avid lesion defined by the blinded readers at one of the acquisition timepoints as an easily identifiable lesion radiologically, where there has been clear focal uptake of ^{68}Ga -OPS202 and 1.5-fold or greater uptake than in the non-tumoural liver and lung parenchyma.
- The SUV_{mean} and SUV_{max} in the primary lesion between each of the three timepoints, measured in the most avid lesions (using the ^{68}Ga -OPS202 scans). This is assessed by the tumour-to-background ratio in the primary tumour and each of the major anatomic sites (liver, lymph nodes, bone, lungs and brain); the background consists of non-tumoural liver parenchyma or aortic blood where sufficient liver is not available. Identification of lesions to be used will be made by one of the two primary readers.

Other Secondary Endpoints:

- Comparison to standard-of-truth for the primary breast tumour:
 - $(^{68}\text{Ga}\text{-OPS202 PET/CT}) / (^{18}\text{F}\text{-FDG-PET/CT})$
 - For each acquisition time of ^{68}Ga -OPS202 PET.

This will be repeated for each of the other anatomical locations:

- Lymph nodes
- Liver
- Axial/appendicular skeleton
- Lungs
- Brain

The second component of the co-primary and appropriate secondary endpoints will also be evaluated on a radioactivity dose MBq/kg of body weight to evaluate if the subject mass has an effect on the diagnostic accuracy.

Exploratory Endpoints:

- Preliminary diagnostic sensitivity of ^{68}Ga -OPS202 imaging sstr2 positive breast cancer tumours by both subject-based and lesion-based analysis compared to standard-of-truth
- SNR calculated from: $\text{SUV}_{\text{mean}}/\text{SUV}_{\text{SD}}$ at the three PET acquisition timepoints using the same lesions as for SUV_{max} . The background will be the same background as for SUV_{max} , of either lesion-free volume of interest (VOI) in the liver or aorta, if insufficient lesion free liver is available
- Estimated correlation in terms of number of avid lesions between ^{68}Ga -OPS202 PET at the agreed “optimum timepoint” and ^{18}F -FDG PET scan. This will be based on lesion counts off the identified optimal timepoint or from the 1-hour timepoint if no optimum is identified
- Estimated correlation between tumour uptake and results of immunohistochemistry staining of sstr2 of the primary tumour.

For further details on efficacy secondary endpoints assessment, refer to the IRC.

(c) Methods and Timing of Assessing, Recording, and Analysing Efficacy Data

Methods for assessing efficacy data are listed below and are described in further detail in the IRC. Timing of efficacy acquisitions are discussed in Section 5. The efficacy data are obtained from the ICL and will be obtained using electronic means. The methods of analyses are discussed in Section 11.4.4.

All images will be sent to a central ICL for QC and central read management. This comprises the following images:

- All ^{68}Ga -OPS202 PET/CT scans
- One ^{18}F -FDG-PET/CT scan.
- One ceCT scan.

The details of the imaging management and read design will be fully described in the IRC. This will include the following:

- Full acquisition guidelines for the site, for IIP and ceCT scan
- Process for PET scanner quality control (phantom assessments and reporting)
- Image transmission methodology
- Core lab QC methodology and management of the images
- Read design for primary endpoint
- Read design for secondary endpoint and process for calculating tumour-to-background ratio and SUV_{mean} and SUV_{max}
- Design of exploratory endpoints
- Conduct of the read
- Management, training and inter-reader evaluation
- Data management
- Data export overview
- Archiving of images.

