1.6 Population to Be Studied

Several types of tumours other than NETs express sstr2 making the imaging of these tumours with peptide receptor radionuclide such as ⁶⁸Ga-OPS202 possible. This study will enrol adult female subjects with newly diagnosed early or advanced breast cancer to detect those expressing sstr2.

To identify the evaluable subjects for the analysis of the primary endpoint, tumours/metastases expressing sstr2 will be identified and documented through the lesion uptake of the diagnostic compound (⁶⁸Ga-OPS202). Only subjects showing tumour ⁶⁸Ga-OPS202 uptake (avid lesion) in target tissues (primary tumour, lymph nodes and/or metastases) higher than non-tumoural liver parenchyma by PET imaging will be selected for the comparison of images at different acquisition timepoints.

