3.2.1 Primary Efficacy Endpoint and Evaluation

- Percentage of subjects with sufficiently avid lesion(s) to be identified as a sstr2 positive lesion. (Avid is defined by the blinded readers at one of the acquisition timepoints as an easily identifiable lesion radiologically, where there has been clear focal uptake of ^{68}Ga -OPS202 and 1.5-fold or greater uptake than the non-tumoural liver and lung parenchyma).
- Differences in the number of lesions detected by ^{68}Ga -OPS202 between the three PET acquisition timepoints (0.5, 1 and 2 hours), and reader interpretation of optimal image(s) in the primary breast lesions.

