7.1 Eligible and Evaluable Subjects

- All subjects who receive ^{68}Ga -OPS202 are “eligible” subjects and will be included in the safety analysis.
- All eligible subjects with one or more readable ^{68}Ga -OPS202 PET and a readable ceCT scan will be included in the first component of the co-primary endpoint analysis to determine sstr2 positive prevalence.
- The following describes those subjects that are eligible and “evaluable” for the second component of the co-primary endpoint to assess the optimum timing of the PET scan following infusion of ^{68}Ga OPS202:
 - A readable ceCT scan
 - At least two ^{68}Ga -OPS202 PET scans that are readable (three images are to be acquired but 2 of these, MUST be readable by the central readers; if only two PET scans are acquired BOTH must be readable) with at least one avid lesion identified by central readers.

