11 STATISTICS

11.1 Analyses Populations

The following population will be used during statistical analyses:

- **Eligibility screened population:** All subjects screened (i.e. who signed the informed consent).
- **Safety population:** All subjects who received the dose of study IIP.
- **⁶⁸Ga-OPS202 screened population:** All subjects who received the dose of study IIP and for whom PET/CT scan images are readable for at least one timepoint. This population encompasses both subjects with sstr2 positive lesion(s) and those with sstr2 negative lesions (no avid lesion with ⁶⁸Ga-OPS202).
- **Sstr2 positive population:** All subjects who received the dose of study IIP and for whom ⁶⁸Ga-OPS202 PET/CT scan images are readable for at least one timepoint and have one avid lesion identified by central readers, ¹⁸F-FDG-PET/CT scan and a ceCT scan confirmed by the central readers.
- **Sstr2 positive evaluable population:** ⁶⁸Ga-OPS202 sstr2 positive population with at least two evaluable ⁶⁸Ga-OPS202 timepoints, ¹⁸F-FDG-PET/CT scan and a ceCT scan confirmed by the central readers.

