11.4.4 Efficacy Evaluation

As indicated in Section 7, the first component of the co-primary endpoint is the percentage of subjects with sufficiently avid lesion(s) to be identified as a sstr2 positive lesion. This will be a simple percentage calculation (number of subjects in sstr2 positive population / number of subjects in ⁶⁸Ga-OPS202 screened population). The second component of the co-primary efficacy variable is the differences in the number of lesions detected by ⁶⁸Ga-OPS202 between the three PET acquisition timepoints (0.5, 1 and 2 hours) in the primary breast lesions. The second component of the co-primary efficacy variable will be summarised by each of the three PET acquisition timepoints (0.5, 1 and 2 hours). The results could identify that one, two or all three timepoints have equal validity for future studies in this population.

As indicated in Section 7, the secondary efficacy variables are the variables measured at Visit 2 after the i.v. administration of the IIP, listed below:

Key Secondary Endpoint:

- Differences in the number of lesions detected by ⁶⁸Ga-OPS202 between the three PET acquisition timepoints (0.5, 1 and 2 hours) and reader interpretation of optimal image(s) in nodular and metastatic lesions. Significant uptake of ⁶⁸Ga-OPS202 for the evaluation of a lesion is an avid lesion defined by the blinded readers at one of the acquisition timepoints as an easily identifiable lesion radiologically, where there has been clear focal uptake of ⁶⁸Ga-OPS202 and 1.5-fold or greater uptake than in the non-tumoural liver and lung parenchyma.
- The SUV_{mean} and SUV_{max} in the primary lesion between each of the three timepoints, measured in the most avid lesions (using the ⁶⁸Ga-OPS202 scans). This is assessed by

the tumour-to-background ratio in the primary tumour and each of the major anatomic sites (liver, lymph nodes, bone, lungs and brain); the background consists of non-tumoural liver parenchyma or aortic blood where sufficient liver is not available. Identification of lesions to be used will be made by one of the two primary readers.

Other Secondary Endpoints:

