3.2.1.1 Primary efficacy analysis

First component of the co-primary endpoint

The first component of the co-primary endpoint is the percentage of subjects with sufficiently avid lesion(s) to be identified as a sstr2 positive lesion, i.e. the sstr2 positive prevalence in this study population. Avid is defined by the blinded readers at one of the timepoints as an easily identifiable lesion radiologically, where there has been clear focal uptake of ⁶⁸Ga-OPS202.

This will be a simple percentage calculation:

$$\begin{aligned} & \text{Percentage of subjects with avid lesion identified as sstr2 positive lesion} \\ &= \frac{\text{Number of subjects in sstr2 positive population}}{\text{Number of subjects in } ^{68}\text{Ga} - \text{OPS202 screened population}} \end{aligned}$$

A listing with the subjects in sstr2 positive population and the subjects in the ⁶⁸Ga-OPS202 screened population will be provided in order to allow computing this percentage.

Second component of the co-primary endpoint

The second component of the co-primary endpoint is based on both image quality and lesion count using the sstr2 positive evaluable population.

The selection of the optimal PET acquisition time will be done by choosing the timepoint with superior images based on overall image quality and observed higher number of lesions detected.

The number of lesions detected by ⁶⁸Ga-OPS202 in the primary breast lesions will be reported at each of the three PET acquisition timepoints (0.5, 1 and 2 hours).

Individual values of number of lesions detected by ⁶⁸Ga-OPS202 in the primary breast lesions (result from both readers as well as final result) will be listed by subject and by PET acquisition timepoint.

Image quality

After blinded reading, the readers will compare the three scans (the three acquisitions of ⁶⁸Ga-OPS202) contemporaneously for each subject and note which image(s), if any, provides superior images based on overall image quality and lesion count.

This qualitative assessment will be performed using a quality score.

For each PET/CT assessment, each independent blinded reader will perform a direct comparison of the three ⁶⁸Ga-OPS202 scans acquired at different times (0.5, 1 and 2 hours) in the primary breast lesions. The readers will be allowed to select whether one, two or all three acquisitions are optimal, attributing a score for each assessment. The readers will be blinded to timepoint sequence.

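### Protocol 7(a)(1) defines the prevalence co-primary differently from Protocol 11.4.4 and the SAP, and the breast-lesion timing co-primary uses an analysis set that does not require a detected breast lesion

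*Protocol*

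**What the plan says.** **First co-primary (prevalence).** Protocol 7(a)(1) explains how the endpoint is calculated. It takes subjects "with primary sstr2 positive lesions identified by" the tracer at any timepoint, "divided by the total number of subjects imaged to obtain the prevalence in this study population". Protocol 3.2.1 names no site: "Percentage of subjects with sufficiently avid lesion(s) to be identified as a sstr2 positive lesion". Protocol 11.4.4 gives the formula as "number of subjects in sstr2 positive population / number of subjects in" the 68Ga-OPS202 screened population, and SAP 3.2.1.1 repeats it. Protocol 11.1 and SAP 2 ask that members of the sstr2 positive population "have one avid lesion identified by central readers", wherever that lesion lies, and that they have the FDG and ceCT scans.

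**Second co-primary (timing).** In SAP 3.2.1.1 the number of lesions "in the primary breast lesions will be reported at each of the three PET acquisition timepoints", and Protocol 11.4.4 has the same breast-only scope. The analysis set is wider. Protocol 7.1 asks for a readable ceCT and at least two readable PET scans "with at least one avid lesion identified by central readers". SAP 2.1.3 wants an avid lesion on at least two timepoints, again at any site. Protocol 1.6 selects women for the timepoint comparison on uptake "in target tissues (primary tumour, lymph nodes and/or metastases", so avidity in nodes alone is enough. The completion rule (Protocol 11.2, SAP 1.3.4) counts 16 evaluable women, at least two with advanced disease, and sets no breast-lesion condition.

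Protocol 3.2 adds another scope: it has the co-primary endpoints measured in the primary tumour and in liver, nodes, bone, lungs and brain. SAP 5, on changes from the protocol, mentions none of these differences.

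**The concern.** A woman with an avid node and a non-avid breast tumour is positive under 11.4.4 and negative under 7(a)(1). A woman who was imaged but has no readable scan is in the denominator of 7(a)(1) and outside that of 11.4.4. A co-primary endpoint should have one definition.

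For timing, the mismatch runs in one direction. A finding that the three timepoints do not differ is an accepted outcome (Protocol 7(a)(2), SAP 3.1.1), and the study hypothesis in Protocol 2.3 is that uptake does not vary with acquisition time. A breast count of 0/0/0 has the same differences as a breast lesion seen equally well on all three scans, yet it says nothing about timing in the breast.

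Excluding resected primaries (Protocol 4.2) ensures that a primary is in place, not that it is detected. The quality score has the same gap. SAP 3.2.1.1 makes it missing only when a scan is non-readable, and scans of equal quality all score 1. No rule covers a breast with nothing detected.

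**Working it through.** **1. The plan's own figure.** Protocol 11.2 plans about 54 women to obtain 16 evaluable: 16/54 = 29.6%. No prevalence is stated, so this is a back-calculation and not a reproduction. An assumed 30% gives 16/0.30 = 53.3, rounded up to 54.

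**2. The two prevalence definitions side by side.**

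| Source | Numerator | Denominator |
|---|---|---|
| Protocol 7(a)(1) | primary lesion positive | all imaged |
| Protocol 11.1 and 11.4.4; SAP 2 and 3.2.1.1 | avid lesion at any site | screened population (readable for at least one timepoint; SAP 2.1.1 also asks for a readable ceCT) |

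**3. When they differ.** Let N be the number imaged, S the number in the screened population (S ≤ N), P the number positive at any site, and k the number of those avid only outside the breast. Assume every positive woman has the FDG and ceCT scans that 11.1 requires. Then 11.4.4 gives P/S and 7(a)(1) gives (P − k)/N. With P above zero, these agree only if k = 0 and S = N.

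**4. Numerator, for illustration.** Take N = S = 54 and P = 16, all evaluable. The documents give no k. Intervals are exact 95%.

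| k | any-site prevalence | primary-lesion prevalence | informative for breast count |
|---|---|---|---|
| 0 | 16/54 = 29.6% | 16/54 = 29.6% (18.0 to 43.6) | 16 |
| 2 | 16/54 = 29.6% | 14/54 = 25.9% (15.0 to 39.7) | 14 |
| 4 | 16/54 = 29.6% | 12/54 = 22.2% (12.0 to 35.6) | 12 |

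Each such woman moves the result by 1/54 = 1.85 percentage points. The last column assumes that a woman avid only outside the breast has no breast lesion counted as detected.

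**5. Denominator, for illustration.** With k = 0, if two of the 54 imaged women had no readable scan (an assumption), 11.4.4 gives 16/52 = 30.8% and 7(a)(1) gives 16/54 = 29.6%.

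**6. Timing comparison.** A 0/0/0 woman has all pairwise differences equal to zero. If the mean difference among the other 16 − k women is d, the mean over all 16 is d × (16 − k)/16. That is 0.875d for k = 2 and 0.75d for k = 4. This applies only where a mean over the evaluable set is taken.

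**7. Size needed for 16 informative women.** At the same rates, the number to image is 16/(14/54) = 61.7, so 62, for k = 2, and 16/(12/54) = 72 for k = 4.

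**The case against.** The other side has a good case on several points.

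- A reader might infer that the plan will produce two rival prevalence results. It will not. Protocol 7(c) refers the reader to 11.4.4 for the analysis methods, and 11.4.4 and the SAP use the same formula. Section 7(a)(1) is a single outlier.
- A reader might infer that node-only women add nothing. They inform the key secondary endpoint in nodal and metastatic lesions. Under Protocol 3.2 they would also inform the co-primary. Step 5 of the read sequence compares the three scans for the primary breast cancer without requiring that it be avid, so a faint primary could still receive a quality score. Whether a breast lesion below the 1.5-fold threshold counts as detected is not stated in either document, and the read design is left to the imaging review charter.
- A reader might infer a measurable dilution of the timing result. After early termination, SAP 5 states that efficacy is no longer summarised in tables. SAP 3.2.1.1 lists breast counts by subject and timepoint, so a 0/0/0 row is visible. Step 6 of the working applies to the by-timepoint summary in Protocol 11.4.4.
- Falling below 16 misses no power or precision target. Protocol 11.2 says that the number does not come from a formal calculation, and no tests are planned.

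All of this limits the size of the point. The conflict remains, because the prevalence percentage and the choice of optimal time both stay in SAP 3.2.1.1, and nothing there says how a woman without a detected breast lesion enters that choice.

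**Conclusion.** The point holds as an inconsistency in definition with a modest and unknown numerical effect. Section 7(a)(1) departs from the rest of the Protocol and from the SAP in numerator and denominator. The results differ if any positive woman is avid only outside the breast, or if any imaged woman falls outside the screened population. Separately, the breast-lesion timing comparison is run in a set that does not require a detected breast lesion, so some women can appear to show no difference without evidence on the question.

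The documents give no share of such women, and zero is possible, in which case the numerator and the informative number do not change. The illustrated range of 29.6% down to 22.2%, and 16 down to 12 informative women, rests on k of 0 to 4 among 16 positive women, all evaluable, with 54 imaged. The 16 is the planned evaluable number. The numerator in 11.4.4 is the sstr2 positive population, which can be larger.

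**What to change.** - **Protocol 7(a)(1):** match 11.4.4 in both numerator and denominator, and report primary-lesion prevalence as a second row over the same denominator.
- **Protocol 3.2:** reconcile its site scope for the co-primaries with 11.4.4.
- **SAP 2.3 and 3.2.1.1:** base the breast-lesion timing comparison on evaluable women with a breast lesion detected on at least one readable timepoint. Asking for one timepoint keeps women whose lesion appears on some scans only, who are the most informative. Set the breast quality score to missing for the other evaluable women, and state how many of the evaluable women are in the comparison.
- **Node-only women:** keep them in the any-lesion prevalence and in the nodal and metastatic analyses.

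The SAP already has a model for this. In SAP 3.2.1.2 the per-organ relative lesion count is limited to subjects with an FDG-detected lesion in that organ.

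The cost is wording and one extra row. The timing set needs no new data, because breast counts are already listed by subject and timepoint for evaluable women. The second prevalence row also needs the breast result for positive women who are not evaluable, and those listings do not cover them. The downside is that the stated informative number may be below 16.
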